#### **Primary Efficacy Endpoint:**

The primary efficacy endpoint is the between-treatment group (Atropine Sulfate Ophthalmic Solution, 0.02% versus Vehicle) difference in the proportion of subjects who show < -0.50 D myopia progression (SER) at the Month 36 visit.

The primary and all secondary endpoints comprise a fixed sequence set of endpoints to be tested in order. A 2-sided significance level of 0.05 will be adopted.

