#### **3.5.1. Atropine Sulfate Ophthalmic Solution, 0.02%**

A Fisher's exact test with a 0.05 two-sided significance level will have 95% power to detect the difference between an Atropine Sulfate Ophthalmic Solution, 0.02% responder proportion of 0.25, and a Vehicle responder proportion of 0.07 when the sample sizes are 136 and 91, respectively.

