#### **3.5.2. Atropine Sulfate Ophthalmic Solution, 0.01%**

A Fisher's exact test with a 0.05 two-sided significance level will have 90% power to detect the difference between an Atropine Sulfate Ophthalmic Solution, 0.01% responder proportion of 0.25, and a Vehicle responder proportion of 0.07 when the sample size in each group is 91.

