## 8.1. Primary Efficacy Endpoint and Analysis

### 8.1.1. Primary Efficacy Endpoint

The primary efficacy endpoint is the between-treatment group (Atropine Sulfate Ophthalmic Solution, 0.02% versus Vehicle) difference in the proportion of subjects' eyes who show less than 0.5 D myopia progression (SER) from baseline at the Month 36 visit.

Spherical equivalent refraction will be measured using cycloplegic autorefractometry at Months 6, 12, 18, 24, 30, and 36. Subjects' eyes will be determined at each visit if they have a less than 0.5 D myopia progression (SER). All data collected through Month 36 will be used, regardless of when treatment is stopped. There will be no imputation for missing data; analysis will be conducted as observed.

The primary analysis will be performed using a Mixed Model based on the binomial distribution using a logit link function. Progression as the dependent variable, subject, treatment, visit, eye (left or right) and baseline age group (as randomized) and SER (as randomized) as independent variables and treatment by visit interaction term included. Random intercepts for subject and eye within subject will be included using variance components and compound symmetry covariance structures, respectively. The primary analysis will be performed using the mITT analysis set assuming data is missing at random.

```
proc glimmix data=master empirical method=quad;  
  class subjid trtpn(ref='0') avisitn eye agegr1 sergr1;  
  model eff(event='1') = trtpn avsitn eye agegr1 sergr1 trtpn*avisitn / dist=bin link=logit solution or;  
  nloptions tech=nrridg maxiter=25;  
  random intercept / subject=subjid type=vc;  
  random intercept / subject=eye(subjid) type=cs;  
  estimate '0.02% vs. Pbo Month 36' trtpn 0 1 -1 trtpn*avisitn 0 0 0 0 0 0 0 0 0 0 1 0 0 0 0 0 -1;
```

The absolute risk difference and associated Wald 95% CI will also be presented at Month 36 using the following frequency procedure.

```
proc freq data=dat order=data;  
  tables trtpn*eff / riskdiff(equal cl=wald);
```

Counts and percentage of subject' eyes progressing at each visit for each stage will be summarized. For the primary endpoint and associated secondary endpoints, Odds Ratios, 95% confidence interval (CI), and p-value will be provided along with an accompanying figure.

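### The primary endpoint is a difference in proportions, but the only model-based effect in SAP 8.1.1 is an odds ratio conditional on child and eye; the planned risk difference is raw and unadjusted

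*SAP*

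**What the plan says.** The Protocol synopsis states the primary endpoint as the between-group "difference in the proportion of subjects who show < -0.50 D myopia progression (SER) at the Month 36 visit". SAP 8.1.1 words it as the "difference in the proportion of subjects' eyes who show less than 0.5 D myopia progression (SER) from baseline at the Month 36 visit". Both are differences in proportions; the unit is the subject in one and the eye in the other.

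The analysis in 8.1.1 is a binomial mixed model with a logit link, fitted by quadrature to the visits from Month 6 to Month 36. "Random intercepts for subject and eye within subject will be included using variance components and compound symmetry covariance structures, respectively". On missing data: "The primary analysis will be performed using the mITT analysis set assuming data is missing at random".

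The outputs in 8.1.1 are of two kinds:

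- **From the model:** the Month 36 contrast on the log-odds scale. For the primary and associated secondary endpoints, "Odds Ratios, 95% confidence interval (CI), and p-value will be provided along with an accompanying figure".
- **Not from the model:** an absolute risk difference at Month 36 with a Wald 95% interval from PROC FREQ, and counts and percentages of eyes by visit. Section 8.1.5 asks again for the unmodelled difference, this time worded for subjects.

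No model-based proportion or difference in proportions is specified. The methods of 8.1.1 are reused for the tertiary responder endpoints in 8.3.1, 8.3.3, 8.3.5 and 8.3.6, and for the exploratory one in 8.4.1.

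**The concern.** With a logit link and random intercepts, the exponentiated contrast compares arms at fixed values of the unobserved child and eye effects. It is a correctly defined quantity, but it is not the odds ratio implied by the response proportions in the arms. It lies further from 1, and the gap grows with the random-effect variance. SAP 6.1 expects the two eyes of a child to be strongly correlated, and the six visits all measure cumulative change from one baseline, so a small variance is unlikely.

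Two things are at stake. First, the odds ratio for tests 1 and 3 of the fixed sequence can be misread as a population effect and set beside the planning rates, where it would look larger than the proportions imply. Second, the p-value and the endpoint-scale effect rest on different footings. The p-value uses all visits, adjusts for the stratification factors and assumes missing at random. The risk difference does none of these: it uses only those observed at Month 36, where the Protocol expects 27% drop-out by the end of Stage 1.

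**Working it through.** **Inputs from the documents.** For 0.02%: "A Fisher's exact test with a 0.05 two-sided significance level will have 95% power to detect the difference", with "0.02% responder proportion of 0.25, and a Vehicle responder proportion of 0.07 when the sample sizes are 136 and 91, respectively". For 0.01%: "0.01% responder proportion of 0.25, and a Vehicle responder proportion of 0.07 when the sample size in each group is 91", stated power 90% (SAP 3.5.2). Drop-out over Stage 1: 27% (Protocol synopsis).

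**Assumptions.** The planning rates are for subjects; I apply them to eyes. The documents give no random-effect variance and no between-eye correlation, so both are shown as assumed values.

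**1. The plan's own figures.** Exact power of the two-sided Fisher test, enumerating all tables, is 95.6% for 136 and 91, and 90.1% for 91 and 91. Both agree with the SAP. The randomised numbers also agree: 125 × 0.73 = 91.25 and 186 × 0.73 = 135.78.

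**2. Population effect at the planning rates.**

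- Difference: 0.25 − 0.07 = 0.18.
- Odds ratio: (0.25/0.75) / (0.07/0.93) = 4.43.

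**3. Conditional odds ratio giving the same proportions.** Let s be the total random-intercept SD (child and eye variances added). For each arm solve E[expit(η + sZ)] = p, with Z standard normal, for p = 0.25 and p = 0.07, using 200-point Gauss-Hermite quadrature. The conditional odds ratio is exp(η₁ − η₀). For example, at s = 3, η₁ = −2.346 and η₀ = −5.158, so exp(2.812) = 16.6.

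| Assumed total SD | Variance | Latent correlation s²/(s² + π²/3) | Conditional odds ratio |
|---|---|---|---|
| 0 | 0 | 0 | 4.43 |
| 1 | 1 | 0.23 | 5.3 |
| 2 | 4 | 0.55 | 8.7 |
| 2.5 | 6.25 | 0.66 | 11.9 |
| 3 | 9 | 0.73 | 16.6 |
| 3.5 | 12.25 | 0.79 | 23.6 |
| 4 | 16 | 0.83 | 33.8 |

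The proportions are 25% and 7% in every row. The usual closed-form attenuation approximation, log OR × √(1 + 0.346 s²), runs high here: 20.45 instead of 16.6 at s = 3. The exact solution should be used.

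**4. Is the middle of the table plausible?** At SD 2.51 the implied ordinary binary correlation between two readings of one eye is 0.34 when both have rate 7%, and 0.45 at 25%. At SD 3.46 it is 0.48 and 0.57. These are not extreme for repeated readings of one eye, but they are not documented either.

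**5. The PROC FREQ interval if the table is run on eyes.** The SAP does not define that data set. With 136 and 91 children and two eyes each:

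- Eyes treated as independent: SE = √(0.25 × 0.75/272 + 0.07 × 0.93/182) = √(0.000689 + 0.000358) = 0.032.
- Between-eye correlation assumed to be 0.8: multiply by √(1 + 0.8) = 1.342, giving 0.043.
- Ratio: 1/1.342 = 0.745, so the naive SE is about 25% too small.

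If the table is run on one result per subject, this last point does not arise.

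**The case against.** The strongest reply is that the plan already reports the effect on the endpoint's own scale: 8.1.1 gives a risk difference with an interval and percentages of eyes at each visit, and 8.1.5 asks for the difference again. A reader can compare those with 25% and 7%. Nothing in 8.1.1 calls the odds ratio the headline result, and a conditional odds ratio is not biased. A footnote would remove most of the risk of misreading.

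Much of this stands. A reader might infer that the plan has no endpoint-scale estimate at all; the two planned risk differences rule that out. A reader might also infer that the planning rates by themselves imply an odds ratio of about 12 to 23. They do not: that range needs a total SD of about 2.5 to 3.5, which appears nowhere in the documents, and at SD 1 the value is only 5.3. Nor do the documents support saying that no other section supplies a model-based proportion. In the copy reviewed, the text of 8.2.1 to 8.2.3 and the opening of 8.1.3 are absent.

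What the reply does not meet is the mismatch. The planned risk difference is unadjusted and leaves out the earlier visits on which the missing-at-random analysis relies. If it is run on eyes, its interval also ignores pairing. A footnote would clarify the odds ratio but would not supply the missing estimate.

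**Conclusion.** The point holds in this limited form. In 8.1.1, and in the visible sections that reuse its method, the only model-based effect is an odds ratio conditional on child and eye. The endpoint-scale effect comes only from a raw Month 36 table. The direction is certain: at the planning rates the conditional odds ratio exceeds 4.43 for any variance above zero. The size is not: it runs from 5.3 to 33.8 for an assumed SD of 1 to 4, with subject-level rates applied to eyes. The understatement of the SE by about 25% depends on an eye-level table and an assumed between-eye correlation of 0.8.

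A reader might go further and conclude that the primary test is compromised. This point gives no ground for that: the contrast, p-value and fixed sequence are untouched. What needs improvement is the reported effect size, and the change is worth making because it is cheap.

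**What to change.** In SAP 8.1.1:

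- Keep the GLIMMIX Month 36 contrast, its p-value and the hierarchy as they are.
- Make the reported effect the standardised Month 36 responder proportion in each arm and their difference, from the same fit. Average predicted probabilities over the fitted random-effect distribution and the observed covariates. Back-transforming the linear predictor with the random effects set to zero is not enough, because that gives another conditional quantity.
- Give a child-clustered 95% interval, for example from a bootstrap that resamples children.
- Label the GLIMMIX odds ratio 'conditional on child and eye'.
- Keep the raw risk difference as a sensitivity analysis, state whether it is per eye or per subject, and give it a child-clustered interval.
- Apply the same to the other responder endpoints that use the 8.1.1 method.

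The cost is SAP wording, additional programming and computing time, since a bootstrap refits a two-level quadrature model many times. The standardised proportions depend on the assumption of normally distributed random effects, which should be stated. The reported effect will also look less impressive than the conditional odds ratio.

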### 8.1.2. Supportive Analysis of Primary Endpoint

#### 8.1.2.1. Subject Composite Result

The supportive efficacy endpoint is the between-treatment group (Atropine Sulfate Ophthalmic Solution, 0.02% versus Vehicle) difference in the proportion of subjects who show less than 0.5 D myopia progression (SER) from baseline at the Month 36 visit without factoring in both eyes within a subject. Subjects with at least one eye that shows less than 0.5 D myopia progression (SER) from baseline will be considered as responders. The supportive analysis will be performed using a Mixed Model based on the binomial distribution using a logit link function. Progression as the dependent variable, subject, treatment, visit, and baseline age group (as randomized) and SER (as randomized) as independent variables and treatment by visit interaction term included. Random intercept for subject will be included using variance components. The supportive analysis will be performed using the mITT analysis set assuming data is

This document is confidential.

methodology for the remaining monotone missing data. The regression model for imputation will include, at a minimum, treatment, visit, eye (left or right) and baseline age group (as randomized) and SER (as randomized), race (Asian vs, non-Asian, see 8.3.13 below), eye color (dark irides versus light irides), and region (U.S. vs. E.U.). This set of imputations will be performed 10 times per evolution for a total of 100 imputations. Missing data from the placebo arm will be imputed according to the normalized placebo SER values, and treatment-related missing data on active arm imputation at each visit will adjusted from the normalized active SER values, up until the normalized placebo SER values at the respective visit in a minimum of 5 steps to assess if a tipping point exists between a statistically significant and a non-significant difference. The imputed datasets will be analyzed using the same model as the primary analysis. The results of these analyses will be combined into a single result using PROC MIANALYZE for each value of the shift. The objective is to determine whether a tipping point exists where the statistical significance between the Atropine Sulfate Ophthalmic Solution, 0.02% and placebo arm will no longer exist.

Treatment-related missing data are data missing because a subject terminates the study prior to the Month 36 visit for the following termination reasons:

- Subject withdrew consent
- Medical reason (AE)
- Physician decision to discontinue treatment
- Death
- Lack of efficacy

Non-treatment related missing data are data missing because a subject terminates the study prior to the Month 36 visit for the following termination reasons:

- Visit missed or telemedicine visit due to COVID-19
- Sponsor terminated study
- Lost to follow-up
- Pregnancy
- Other

#### 8.1.4. COVID-19 Analyses

Data that is missing due to subject unable to go to the investigator's office due to COVID-19 are considered missing at random. The Mixed Model analysis being used in the primary analysis is known to be robust in dealing with data that is missing at random. Therefore, no additional sensitivity analyses will be performed involving data missing due to COVID-19.

#### 8.1.5. Other Analysis of the Primary Endpoint

The primary analysis will be repeated for the ITT and PPS analysis sets and for each stratification level. Sensitivity analyses will be repeated for the ITT population only. There will be no imputation for missing data; analysis will be conducted as observed. The analysis will be conducted using the same model as the primary efficacy analysis (as described in 8.1.1 above).

As part of the sensitivity analyses for the primary efficacy analysis, the point estimate and 95% Wald confidence interval, for the absolute difference in the proportions of subjects with less than 0.50D myopia progression (SER) at Month 36 between the treatment groups without any models should be presented.

This document is confidential.

8.2.4. Between-treatment group (Atropine Sulfate Ophthalmic Solution, 0.02% versus Vehicle)  
Difference in the Mean Change from Baseline in Axial Length at Month 36

A secondary analysis will be performed on the between-treatment group (Atropine Sulfate Ophthalmic Solution, 0.02% versus vehicle) difference in the mean change from baseline in axial length at the Month 36 visit. The analysis method will be the same as the secondary efficacy analysis as described in 8.2.1 above.

Summary statistics will be presented along with a full data listing by treatment group.

8.2.5. Between-treatment Group (Atropine Sulfate Ophthalmic Solution, 0.01% Versus Vehicle)  
Difference in Mean Change from Baseline in Axial Length at the Month 36 Visit

A secondary analysis will be performed on the between-treatment group (Atropine Sulfate Ophthalmic Solution, 0.1% versus vehicle) change from baseline in axial length at the Month 36 visit. The analysis method will be the same as the secondary efficacy analysis as described in 8.2.1 above using the updated statement:

*estimate '0.01% vs. Pbo Month 36' trtpn 1 0 -1 trt01pn\*avisitn 0 0 0 0 1 0 0 0 0 0 0 0 0 0 0 -1 0/ cl ;*

Summary statistics will be presented along with a full data listing by treatment group.

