**8.3. Tertiary Efficacy Endpoint(s) and Analyses**

8.3.1. Between-treatment Group (Atropine Sulfate Ophthalmic Solution, 0.02% Versus Vehicle)  
Difference in the Proportion of Subjects' eyes who Show less than 0.5 D Myopia Progression (SER) From Baseline at the Month 24 and Month 12 visits

A tertiary analysis will be performed on between-treatment group (Atropine Sulfate Ophthalmic Solution, 0.02% Versus Vehicle) difference in the proportion of subjects' eyes who show less than 0.5 D myopia progression (SER) from baseline at the Month 24 and Month 12 visits. The analysis method will be the same as the primary efficacy analysis as described in 8.1.1 above using the updated statements:

*estimate '0.02% vs. Pbo Month 12' trtpn 0 1 -1 trtpn\*avisitn 0 0 0 0 0 0 1 0 0 0 0 0 -1 0 0 0 0 0*  
*trt01pn\*agegr1 0 0 0 1 0 -1;*

*estimate '0.02% vs. Pbo Month 24' trtpn 0 1 -1 trtpn\*avisitn 0 0 0 0 0 0 0 0 1 0 0 0 0 0 -1 0 0 0;*

Summary statistics and figure will be presented along with a full data listing by treatment group.

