8.3.6. Between-treatment Group (Atropine Sulfate Ophthalmic Solution, 0.01% versus Vehicle)  
Difference in the Proportion of Subjects' Eyes who Show less than 0.75 D Myopia  
Progression (SER) From Baseline at the Month 36 Visit

A tertiary analysis will be performed on the between-treatment group (Atropine Sulfate Ophthalmic Solution, 0.01% versus vehicle) difference in the proportion of subjects' eyes who show less than 0.75 D myopia progression (SER) from baseline at the Month 36 visit. The analysis method will be the same as the primary efficacy analysis as described in 8.1.1 above using the updated statement:

*estimate '0.01% vs. Pbo Month 36' trtpn 1 0 -1 trtpn\*avisitn 0 0 0 0 1 0 0 0 0 0 0 0 0 0 0 -1 0 ;*

Summary statistics will be presented along with a full data listing by treatment group.

This document is confidential.

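### SAP contrast code: the 0.01% Month 36 and high-myopia vectors are wrong under any visit order, and the primary vector is Month 36 only under an order not stated

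*SAP*

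**What the plan says.** SAP 8.1.1 lists six post-baseline visits: "Spherical equivalent refraction will be measured using cycloplegic autorefractometry at Months 6, 12, 18, 24, 30, and 36". The fixed effects in its PROC GLIMMIX model are "trtpn avsitn eye agegr1 sergr1 trtpn*avisitn". The primary contrast, labelled 0.02% against placebo at Month 36, is written by position as "trtpn 0 1 -1 trtpn*avisitn 0 0 0 0 0 0 0 0 0 0 1 0 0 0 0 0 -1".

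Section 8.2.5 (0.01% against vehicle, axial length, Month 36) takes its method from 8.2.1 and supplies its own statement. That statement begins "trtpn 1 0 -1 trt01pn" and ends with the coefficients "0 0 0 0 1 0 0 0 0 0 0 0 0 0 0 -1 0/ cl". Section 8.3.6 (0.01%, 0.75 D responders, Month 36) uses the 8.1.1 model with the same coefficients, "0 0 0 0 1 0 0 0 0 0 0 0 0 0 0 -1 0".

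Sections 8.3.1 to 8.3.4 give Month 12 and Month 24 statements. The 0.02% Month 12 vector is "0 0 0 0 0 0 1 0 0 0 0 0 -1 0 0 0 0 0", and in 8.3.1 it is followed by a treatment-by-age part, "agegr1 0 0 0 1 0 -1". Section 8.3.12 (high myopia) prints three Month 36 statements: overall, Low and High.

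Section 8 makes the primary and five secondary endpoints a fixed sequence at two-sided 0.05. The 8.2.5 comparison is the last of the six.

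**The concern.** A positional ESTIMATE statement means only what the order of the class levels makes it mean. If the order is not fixed, or a coefficient is in the wrong place, the label and the tested hypothesis part company.

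Two confirmatory tests are touched. For 0.01% axial length, the printed statement has no usable contrast and would have to be re-specified when the analysis is run. For the primary endpoint, the prose says Month 36 but the code does not settle which month is tested. One natural ordering would put a Month 30 odds ratio, confidence interval and p-value under a Month 36 label.

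**Working it through.** **Inputs.** Three treatment levels. `ref='0'` on `trtpn` is taken to place vehicle last, which fits the printed treatment coefficients 0 1 -1 (0.02% against vehicle) and 1 0 -1 (0.01% against vehicle). Six visits (8.1.1); the protocol schedule puts axial length at the same six. Visit varies fastest in `trtpn*avisitn`.

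**Cell map.** 3 × 6 = 18 cells: 0.01% in 1–6, 0.02% in 7–12, vehicle in 13–18.

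**Where the non-zero coefficients fall.** Text order is the order 12, 18, 24, 30, 36, 6.

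| Section and label | Entries | +1 / -1 at | Numeric order | Text order |
|---|---|---|---|---|
| 8.1.1, 0.02% Month 36 | 17 | 11 / 17 | Month 30 vs 30 | Month 36 vs 36 |
| 8.2.5 and 8.3.6, 0.01% Month 36 | 17 | 5 / 16 | Month 30 vs 24 | Month 36 vs 30 |
| 8.3.1, 8.3.2, 0.02% Month 12 | 18 | 7 / 13 | Month 6 vs 6 | Month 12 vs 12 |
| 8.3.1, 8.3.2, 0.02% Month 24 | 18 | 9 / 15 | Month 18 vs 18 | Month 24 vs 24 |
| 8.3.3, 8.3.4, 0.01% Month 12 | 18 | 1 / 13 | Month 6 vs 6 | Month 12 vs 12 |
| 8.3.3, 8.3.4, 0.01% Month 24 | 18 | 3 / 15 | Month 18 vs 18 | Month 24 vs 24 |
| 8.3.12, 0.02% Month 36 | 19 | 13 / 19 | +1 in a vehicle cell, -1 outside the effect | same |

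Of these seven distinct vectors, none matches its label in numeric order and five match in text order. The other two match in none of the 720 possible orders. The primary matches in 120 of the 720, namely those with Month 36 fifth (5! = 120).

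**Can another visit count rescue the 0.01% vector?** The same visit in the first and third arm blocks lies 2v cells apart, where v is the number of visits. Here 16 − 5 = 11, so v = 5.5. No whole number works.

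**Estimability.** With intercept, treatment, visit and interaction in the model, each arm's coefficient must equal the sum of its cell coefficients, and each visit's coefficient must equal the sum of that visit's cells across arms. None of the statements gives a visit main-effect coefficient, so each visit sum must be zero.

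- 8.1.1: visit 5 gives +1 − 1 = 0; 0.02% gives +1; vehicle gives −1. All agree, so it is estimable.
- 8.2.5 and 8.3.6: visit 5 gives +1 and visit 4 gives −1, where both should be 0. Not estimable.
- 8.3.12: the 0.02% arm has coefficient +1 but no non-zero cell among 7–12, and vehicle has −1 but a cell sum of +1. Not estimable.

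**Other faults in the same code.**

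- In 8.3.12 the Low and High three-way parts have 9 and 8 entries for 3 × 6 × 2 = 36 cells. Both have +1 at position 2 and −1 at position 8, so after zero padding they are one vector and cannot separate the strata. Both name `blmymop`, which is not in that model.
- Section 8.3.12 is headed 0.01% but prints only 0.02% statements.
- The 8.3.1 Month 12 statement adds a treatment-by-age term that the 8.1.1 model does not contain.
- `avsitn` stands for `avisitn` in the 8.1.1 and 8.3.12 models, and 8.2.5 uses both `trtpn` and `trt01pn`.

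**Count of printed statements.** 8.1.1 (1) + 8.2.5 (1) + 8.3.1 to 8.3.4 (2 each, 8) + 8.3.6 (1) + 8.3.12 (3) = 14. Wrong under any order: 1 + 1 + 3 = 5. Off-model term: 1. Dependent on order only: 14 − 5 − 1 = 8.

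**The case against.** The best defence concerns the primary. Sorting the labels Month 6 to Month 36 as text gives exactly 12, 18, 24, 30, 36, 6, and under that order the primary, Month 12 and Month 24 vectors are all right. That is good internal evidence of the coding intended, so the primary point is a missing specification and not a proven error. This stands. But the only visit list in 8.1.1 is chronological, the text available gives no order or format for `avisitn` in the model, and the numeric reading yields an estimable contrast that nobody would be prompted to query.

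On 8.2.5, restoring one zero before the −1 gives 18 entries with non-zeros at 5 and 17, the correct contrast under text order. A dropped zero is the likely cause. Loss in PDF reading cannot be fully excluded, but the same string in 8.3.6 makes copying from one section to the other more likely. It is still wrong as written.

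It is also fair that the prose and labels leave the intended hypothesis clear, that the 8.2.5 failure should be visible (a non-estimable or rejected statement, not a wrong number), that no later confirmatory test depends on step 6, and that program QC is planned in section 14. Against this, the SAP directs analysts to use these statements and does not call them illustrative. A confirmatory contrast should not have to be repaired at analysis.

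**Conclusion.** The concern holds. Of 14 printed statements, 5 (8.2.5, 8.3.6 and three in 8.3.12) cannot give the labelled contrast under any visit order, and one (8.3.1 Month 12) carries an off-model term. The remaining 8, including the primary, are right in text order and one visit (6 months) early in numeric order. In the fixed sequence, test 6 is affected for certain and test 1 conditionally.

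This rests on vehicle being the last treatment level and on six visits in the model. The code for 8.2.1 to 8.2.3 is not in the text available, so tests 2 to 5 are not judged. For 8.2.5, non-estimability assumes the fixed effects that the protocol synopsis gives for continuous endpoints (treatment, visit and their interaction). For 8.3.6 it follows from the model printed in 8.1.1, once `avsitn` is corrected.

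**What to change.** Replace the positional vectors with contrasts that name their levels: LSMEANS or LSMESTIMATE differences, or non-positional ESTIMATE statements naming the treatment and Month 36. These are right under any visit order.

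If positional code is kept, state the `avisitn` order in the SAP and give full 18-entry vectors that match it. Month 36 is then:

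- numeric order: cells 12 and 18 for 0.02%, cells 6 and 18 for 0.01%;
- order 12, 18, 24, 30, 36, 6: cells 11 and 17 for 0.02%, cells 5 and 17 for 0.01%.

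Either way:

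- correct 8.2.5, 8.3.6 and 8.3.12;
- give 8.3.12 distinct Low and High contrasts on the model's own SER-group variable, and add the 0.01% contrasts its heading promises;
- remove the treatment-by-age part from 8.3.1;
- correct `avsitn`, `trt01pn` and `blmymop`;
- check the code in 8.2.1 to 8.2.3 in the same way.

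The cost is an edit to SAP code. Data, participants and design are unaffected.
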